6.3 Populations for Analyses

- Enrolled participants: All participants who signed informed consent and were registered into IRT.
- All treated participants: All participants who received at least one dose of any study medication, including placebo doses.
- All randomized participants: All participants who are randomized to any treatment group.
- PK: All randomized participants with available serum time-concentration data.

7 STATISTICAL ANALYSES

7.1 General Methods

Unless otherwise noted, the bulleted titles in the following subsections describe tabulations of discrete variables, by the frequency and proportion of subjects falling into each category, grouped by treatment (with total). Percentages given in these tables will be rounded and, therefore, may not always sum to 100%.

Continuous variables will be summarized by treatment group (with total, as needed) using the mean, standard deviation, median, quartiles, minimum and maximum values, unless specified otherwise.

7.2 Study Conduct

7.2.1 Participant Disposition

Pre-Randomized (Before Double-blind Period) Subject Status and Subject Status on treatment will be summarized. A participant listing for all randomized participants will be provided showing the participant’s randomization date, first and last dosing date, off treatment date and reason for going off-study treatment. Information regarding off-study reason will be included if available.

7.2.2 Demographic and Baseline Characteristics

Listings will be provided for demographic characteristics (including age, race and gender) for all treated participant.

7.2.3 Medical History

Not applicable (not required for a synoptic CSR)

7.2.4 Prior Therapy

Not applicable (not required for a synoptic CSR)

7.3 Extent of Exposure

A listing of study medication received will be provided for all treated participants.

[REDACTED]

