### **Overall Design:**

This is a Phase 3, randomized, study of BMS-986205 in combination with nivolumab versus nivolumab monotherapy in adult and adolescent participants with unresectable or metastatic melanoma that is previously untreated. (This study was originally double blind with respect to BMS-986205 but was unblinded with Revised Protocol 01.)

- A pre-treatment tumor sample to determine PD-L1 status is required to be submitted from all participants prior to randomization. The sample must be obtained within 3 months prior to enrollment from a metastatic tumor lesion or from an unresectable primary tumor lesion; the tumor sample must be taken from a site of disease that has not been previously irradiated. In addition, no intervening treatment may have been administered between the time of biopsy/surgery and randomization.
- Participants must have a documented BRAF status prior to randomization.
- Depending on the treatment arm, the participant will receive BMS-986205 plus nivolumab or nivolumab monotherapy for up to 104 weeks (approximately 2 years) of study treatment. Under Revised Protocol 01, BMS-98205 Placebo will not be administered to Arm B participants, and investigators have the option of continuing on nivolumab monotherapy in participants assigned to Arm A (nivolumab + BMS986205).
- One cycle of treatment is defined as 4 weeks. Treatment will continue until investigator-assessed disease progression per RECIST v1.1 criteria, unacceptable toxicity, withdrawal of consent/assent, or completion of 104 weeks of treatment, whichever occurs first. Treatment beyond initial progression is permitted if the participant has investigator-assessed clinical benefit, is tolerating study treatment (see [Sections 8.1.1](#) and [8.1.3.2](#) of the protocol), and has not yet completed 104 weeks of study treatment.
- On-study tumor assessments will follow the schedule of the local standard of care.

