**Figure 1-1: Study Schematic**

Note: As of Revised Protocol 01, treatment will no longer be blinded, and participants in Arm B will no longer receive BMS-986205 Placebo. Participants in Arm A, have the option to discontinue BMS-986205, and continue nivolumab monotherapy, at investigator discretion.

During the treatment phase, participants will receive:

- In Arm A: BMS-986205 100 mg PO QD and Nivolumab 480 mg IV Q4W for a maximum of 104 weeks. Under Revised Protocol 01 investigators have the option of continuing participants on nivolumab monotherapy.
- In Arm B: BMS-986205 Placebo PO QD and Nivolumab 480 mg IV Q4W for a maximum of 104 weeks. Under Revised Protocol 01 BMS-986205 Placebo should not be administered.

Dose reductions are not permitted for nivolumab. One dose reduction is permitted for BMS-986205, from a 100 mg QD tablet to a 50 mg QD tablet. No re-escalation is permitted after dose reduction. BMS-986205 tablets must be taken by mouth, and swallowed whole and intact. Crushing, chewing, dissolving, and other alterations to the formulation or route of administration are not permitted.

Doses of BMS-986205 and nivolumab should be delayed due to treatment-related AEs described in [Section 7.4.3](#) of the protocol. Treatment-related AEs resulting in permanent discontinuation of study treatment are described in [Section 8](#) of the protocol. Treatment may be prematurely discontinued due to unacceptable toxicity, withdrawal of consent, disease progression, or completion of treatment cycles, whichever occurs first. A Data Monitoring Committee (DMC) will provide independent oversight of safety, study conduct and efficacy of the study treatments.

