## 10.1 Sample Size Determination

**Per Revised Protocol 01 this section is not applicable.**

The sample size is calculated in order to compare PFS between participants randomized to receive BMS-986205 with nivolumab vs nivolumab monotherapy. The number of events required is simulated based on results from Study CA209067; this simulation resulted in a median PFS of 6.9 months for nivolumab monotherapy and 11.8 months for BMS-986205 with nivolumab therapy, incorporating 35% of participants with durable response in the combined groups, and a non-proportional hazard resulting in an effective hazard ratio (HR) of approximately 0.73.

Based on these assumptions, the study requires at least 365 PFS events to ensure approximately 85% power to detect an HR of 0.73 with an overall type I error of 0.05 (two-sided). Approximately 700 participants will be randomized to the 2 treatment arms in a 1:1 ratio. While follow-up for the primary PFS endpoint is planned to occur when 365 participants have had a PFS event, the follow-up for the primary PFS endpoint can also be terminated 9 months after the randomization of the last participant if the 365th event has not occurred (e.g. slow arrival of events close to but less than 365 that suggest a higher than expected long-term response rate). Predictions for enrollment and follow-up are based on an estimation of approximately 12 months for enrollment and 7 months of follow-up after the end of enrollment. Various patterns of enrollment were assessed from uniform enrollment to enrollment of 25% of participants in the first half of enrollment and 75% in the second half of enrollment.

Follow-up for the overall survival (OS) endpoint is planned to occur when 330 participants have had an OS event. If the 330th event has not occurred at 24 months after randomization of the last participant, then the follow-up time can be terminated 24 months after the randomization of the last participant. A total of 330 OS events would provide approximately 90% power to detect an overall HR of approximate 0.70 with a type I error of 0.05 (two-sided).

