7.5.2 Serious Adverse Events

Serious adverse events will be summarized by treatment group:

- Overall summary of SAEs by worst CTC grade (any grade, grade 3-4, grade 5) presented by SOC/PT.
- Overall summary of drug-related SAEs by worst CTC grade (any grade, grade 3-4, grade 5) presented by SOC/PT.

All analyses will be conducted using the 30-day safety window.

A by-subject SAE listing will be provided for the “enrolled subjects” population.

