7.5.4 Adverse Events

Adverse events will be summarized by treatment group.

The following analyses will be conducted using the 30 days safety window:

- Overall summary of any AEs by worst CTC grade (1, 2, 3, 4, 5, not reported, total) presented by SOC/PT.
- Overall summary of drug-related AEs by worst CTC grade (any grade, grade 3-4, grade 5) presented by SOC/PT.

A by-subject AE listing will be provided.

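### The by-arm AE and SAE tables in the readable SAP are crude proportions over a window that lengthens with time on treatment, with no exposure-adjusted rate beside them

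*SAP*

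**What the plan says.** - **Form of the tables.** SAP 7.1 presents discrete variables "by the frequency and proportion of subjects falling into each category, grouped by treatment (with total"). SAP 7.5.4 applies this to AEs: "Overall summary of any AEs by worst CTC grade (1, 2, 3, 4, 5, not reported, total) presented by SOC/PT". SAP 7.5.2 does the same for serious events: "Overall summary of SAEs by worst CTC grade (any grade, grade 3-4, grade 5) presented by SOC/PT". Both sections add drug-related versions, and both are by treatment group.
- **Counting window.** SAP 6.1.2 starts the on-treatment period at first dose and ends it 30 or 100 days after the last dose, depending on the analysis. SAP 7.5.2 chooses the shorter: "All analyses will be conducted using the 30-day safety window". SAP 7.5.4 uses 30 days as well.
- **Time on treatment.** Protocol synopsis, Overall Design: "Treatment will continue until investigator-assessed disease progression per RECIST v1.1 criteria, unacceptable toxicity, withdrawal of consent/assent, or completion of 104 weeks of treatment", whichever comes first. Treatment beyond progression is allowed under conditions.
- **Arm-specific change.** Under Revised Protocol 01 placebo stops in Arm B, and "Participants in Arm A, have the option to discontinue BMS-986205, and continue nivolumab monotherapy, at investigator discretion".
- **Exposure.** The readable text of SAP 7.3 is one sentence: "A listing of study medication received will be provided for all treated participants". A redaction follows, and the next readable heading is 7.3.2.
- **Related listings.** SAP 7.2.1 lists first and last dosing dates and the off-treatment date for all randomized participants. SAP 7.5.2 and 7.5.4 add by-subject SAE and AE listings.

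**The concern.** Every treated participant counts as one in the denominator, whether at risk for two months or for two years. With the same underlying event rate in both arms, the arm treated for longer shows the higher percentage. Efficacy analyses have been dropped, so the by-arm safety tables are the main comparative display left. A reader who sees more events in one arm cannot tell from the specified AE and SAE tables whether the drug is more toxic or the participants were simply observed for longer. In Arm A, time on nivolumab and time on BMS-986205 can also diverge after Revised Protocol 01.

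**Working it through.** **1. The plan's own figures.** The only computable design figures are in Protocol 10.1, which is marked not applicable. With 1:1 allocation and two-sided 0.05, power = Φ(√d · |ln HR| / 2 − 1.96).
- PFS: d = 365, HR 0.73 gives 0.852 (stated: about 85%).
- OS: d = 330, HR 0.70 gives 0.900 (stated: about 90%).

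Both reproduce and neither is in dispute. They do not bear on the safety tables.

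**2. Inputs for an illustration of scale.**
- Time to progression as a stand-in for time on treatment: "median PFS of 6.9 months for nivolumab monotherapy and 11.8 months for BMS-986205 with nivolumab therapy" (Protocol 10.1). In years, m = 6.9/12 = 0.575 and 11.8/12 = 0.983.
- Durable responders: 35%. Protocol 10.1 states this for the combined groups; applying it to each arm is an assumption.
- Cap C = 104 × 7 / 365.25 = 1.993 years. Tail w = 30 / 365.25 = 0.082 years.
- AE hazard λ, constant and **identical in both arms**: 0.1, 0.3 and 1.0 per year. These are assumed, because the documents give no AE rates.

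**3. Formulas.** Progression-free probability: S(t) = 0.35 + 0.65·exp(−θt). Setting S(m) = 0.5 gives θ = −ln(0.15/0.65)/m = 1.466/m, which is 2.550 (Arm B) and 1.491 (Arm A) per year. Time on treatment is T = min(progression, C), and time at risk is T + w.

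Crude incidence = 1 − E[exp(−λ(T + w))], where the expectation is

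0.35·exp(−λ(C + w)) + 0.65·exp(−λw)·{ θ/(θ+λ)·[1 − exp(−(θ+λ)C)] + exp(−(θ+λ)C) }.

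At λ = 1.0:
- Arm B: 1 − (0.0439 + 0.5988 × 0.7185) = 0.526.
- Arm A: 1 − (0.0439 + 0.5988 × 0.6014) = 0.596.

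**4. Results.** Mean time on treatment is 11.4 months (Arm B) and 13.3 months (Arm A).

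| λ per year | Arm B | Arm A | Gap (points) |
|---|---|---|---|
| 0.1 | 9.5% | 11.0% | 1.5 |
| 0.3 | 24.5% | 28.1% | 3.7 |
| 1.0 | 52.6% | 59.6% | 7.0 |

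Gaps are taken before rounding. The true hazard ratio is 1 throughout. Expected time to first event or window end is incidence/λ, so first events per person-time return λ in each arm and their ratio is 1.00.

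**5. Sensitivity.**
- Equal durations: gap 0.
- Medians 8.0 vs 6.9 months, 35% durable, hazards 0.01 to 0.20 per month: 0.4 to 2.0 points.
- All AE risk in the first 3 months (exponential durations, medians 11.8 vs 6.9, hazards 0.05 to 0.20 per month): 0.3 to 1.0 points.
- Exponential durations with HR 0.73 (6.9 vs 6.9/0.73 = 9.45 months), λ as in step 4: 1.7, 4.0 and 6.6 points.
- Exponential durations at medians 6.9 and 11.8, λ as in step 4: 7.9% vs 10.7%, 20.9% vs 27.6% and 49.1% vs 60.1%, or about 3 to 11 points. This implies HR 6.9/11.8 = 0.58, well away from the stated 0.73, so it should not be the headline.

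**The case against.** Four points on the other side carry weight.

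- **Redaction.** A reader might infer that exposure is only listed and that no person-time denominator by arm is planned. The documents do not support that. Text is blacked out after the one readable sentence of SAP 7.3, and the jump to heading 7.3.2 suggests a hidden subsection. What can be said is narrower: the AE and SAE table specifications in 7.5.2 and 7.5.4 are readable, and they contain no rate.
- **Descriptive purpose.** Protocol 10.3.2 asks for descriptive worst-grade tables by treatment group, and the SAP delivers them for a synoptic report. No between-arm safety test is visible. The share of participants with an event during treatment plus 30 days is a legitimate quantity. The risk is misreading, not an invalid inference.
- **Raw material exists.** The dosing-date and by-subject event listings would let a reader derive time at risk by hand. That is true, but no such analysis is specified in the readable text.
- **Scale.** A reader might also infer an actual distortion of up to 11 points. That figure needs the exponential model with HR 0.58. Every version also rests on superseded medians, assumed hazards and PFS standing in for time on treatment, although toxicity stopping and treatment beyond progression both break that link. No exposure imbalance has been shown.

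**Conclusion.** The point stands as a conditional one. The readable AE and SAE tables are crude proportions over a window that grows with time on treatment. If that time differs by arm, they mix duration with toxicity, and the longer-treated arm looks worse. A reasonable scale is 1.5 to 7.0 percentage points. That range assumes the superseded planning medians, 35% durable responders in each arm, and a constant and equal hazard between 0.1 and 1.0 per year. The actual size is unknown, since neither the numbers treated nor the exposure by arm are given. The documents do not support the stronger readings that the plan lacks any exposure summary or that the safety comparison is invalid. The change is a worthwhile improvement, not the correction of an error.

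**What to change.** - **SAP 7.5.2 and 7.5.4.** Keep the crude percentages. Beside them, by arm, add participants with a first event per 100 patient-years at risk (to first event or end of the 30-day window), for any AE, Grade 3-5 AEs, SAEs and drug-related events.
- **SAP 7.3.** If the redacted text does not already provide it, add a by-arm summary of time on nivolumab and, separately, time on BMS-986205 or placebo.
- **Definition.** State which drug's last dose closes the window when a participant in Arm A stops BMS-986205 and stays on nivolumab. The readable text of SAP 6.1.2 refers only to study treatment.

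The cost is one summary table and one extra column, from dosing and onset dates that the SAP already plans to list; no new data are needed. The downside is that the rates assume a roughly constant hazard, which early-onset events would violate. They therefore supplement the crude percentages and do not replace them.

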7.3.2 Subsequent Anti-Cancer Therapy

Not applicable (not required for a synoptic CSR)

[REDACTED]

7.5 Safety

The safety analysis will be presented in all treated participants, unless otherwise specified.

7.5.1 Deaths

A list of death will be provided for all enrolled participants.

7.5.2 Serious Adverse Events

Serious adverse events will be summarized by treatment group:

- Overall summary of SAEs by worst CTC grade (any grade, grade 3-4, grade 5) presented by SOC/PT.
- Overall summary of drug-related SAEs by worst CTC grade (any grade, grade 3-4, grade 5) presented by SOC/PT.

All analyses will be conducted using the 30-day safety window.

A by-subject SAE listing will be provided for the “enrolled subjects” population.

7.5.3 Adverse Events Leading to Discontinuation of Study Therapy

A list of adverse events leading to discontinuation of study therapy will be provided for all treated participants.

7.5.4 Adverse Events

Adverse events will be summarized by treatment group.

The following analyses will be conducted using the 30 days safety window:

- Overall summary of any AEs by worst CTC grade (1, 2, 3, 4, 5, not reported, total) presented by SOC/PT.
- Overall summary of drug-related AEs by worst CTC grade (any grade, grade 3-4, grade 5) presented by SOC/PT.

A by-subject AE listing will be provided.

7.5.5 Laboratory Parameters

Laboratory parameters including hematology, serum chemistry, liver function, and renal function in SI units will be summarized using worst grade by treatment group for all treated participants.

A by-subject listing of these laboratory parameters will be provided.

[REDACTED]

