### **9.2.7 Laboratory Test Result Abnormalities**

The following laboratory test result abnormalities should be captured on the non-serious AE CRF page or SAE Report Form electronic, as appropriate. Paper forms are only intended as a back-up option when the electronic system is not functioning.

- Any laboratory test result that is clinically significant or meets the definition of an SAE
- Any laboratory test result abnormality that required the participant to have study treatment discontinued or delayed/ interrupted
- Any laboratory test result abnormality that required the participant to receive specific corrective therapy

It is expected that wherever possible, the clinical rather than laboratory term would be used by the reporting investigator (eg, anemia versus low hemoglobin value).

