#### 10.3.2 Safety Analyses

All safety analyses will be performed on the Safety Population.

Endpoint	Statistical Analysis Methods
Primary	Safety analyses will be performed in all treated participants. Descriptive statistics of safety will be presented using National Cancer Institute (NCI) Common Terminology Criteria for Adverse Events (CTCAE) version 4.03 by treatment group. All on-study AEs, treatment-related AEs, SAEs, and treatment-related SAEs will be tabulated using worst grade per NCI CTCAE v 4.03 criteria by system organ class and preferred term. On-study lab parameters including hematology, chemistry, liver function, and renal function will be summarized using worst grade NCI CTCAE v 4.03 criteria.
Exploratory	Additional safety analyses will be described in the SAP finalized before database lock.

[REDACTED]

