### APPENDIX 3      **ADVERSE EVENTS AND SERIOUS ADVERSE EVENTS: DEFINITIONS AND PROCEDURES FOR RECORDING, EVALUATING, FOLLOW UP AND REPORTING**

#### **ADVERSE EVENTS**

Adverse Event Definition:
An Adverse Event (AE) is defined as any new untoward medical occurrence or worsening of a preexisting medical condition in a clinical investigation participant administered study treatment and that does not necessarily have a causal relationship with this treatment.
An AE can therefore be any unfavorable and unintended sign (such as an abnormal laboratory finding), symptom, or disease temporally associated with the use of study treatment, whether or not considered related to the study treatment.
Events Meeting the AE Definition

• Any abnormal laboratory test results (hematology, clinical chemistry, or urinalysis) or results from other safety assessments (eg, ECG, radiological scans, vital signs measurements), including those that worsen from baseline, considered clinically significant in the medical and scientific judgment of the investigator. Note that abnormal lab tests or other safety assessments should only be reported as AEs if the final diagnosis is not available. Once the final diagnosis is known, the reported term should be updated to be the diagnosis.

• Exacerbation of a chronic or intermittent pre-existing condition including either an increase in frequency and/or intensity of the condition.

• New conditions detected or diagnosed after study intervention administration even though it may have been present before the start of the study.

• Signs, symptoms, or the clinical sequelae of a suspected drug-drug interaction.

• Signs, symptoms, or the clinical sequelae of a suspected overdose of either study intervention or a concomitant medication. Overdose, as a verbatim term (as reported by the investigator), should not be reported as an AE/SAE unless it is an intentional overdose taken with possible suicidal/self-harming intent. Such overdoses should be reported regardless of sequelae and should specify "intentional overdose" as the verbatim term

Events NOT Meeting the AE Definition

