3.1.1 Safety

Safety will be analyzed through the incidence of deaths, adverse events, serious adverse events, adverse events leading to discontinuation, adverse events leading to dose modification, and specific laboratory abnormalities (worst grade) in each treatment arm. Toxicities will be graded using the National Cancer Institute (NCI) Common Terminology Criteria for Adverse Events (CTCAE) version 4.03.

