6 STUDY PERIODS, TREATMENT REGIMENS AND POPULATIONS FOR ANALYSES

6.1 Study Periods

6.1.1 *Baseline Period*

Baseline evaluations or events will be defined as evaluations or events that occur before the date and time of the first dose of study treatment. Evaluations on the same date and time of the first dose of study treatment will be considered as baseline evaluations. For subjects who are randomized but not treated, baseline evaluation will be defined as those that occur before the date and time of randomization.

In cases where the time (onset time of event or evaluation time and dosing time) is missing or not collected, the following definitions will apply:

- Pre-treatment AEs will be defined as AEs with an onset date prior to but not including the day of the first dose of study treatment
- Baseline evaluations (laboratory tests, pulse oximetry and vital signs) will be defined as evaluations with a date on or prior to the day of first dose of study treatment

If there are multiple valid assessments, the assessment that is closest to day (and time if collected) of the first dose of study treatment will be used as the baseline in the analyses. If multiple assessments are collected at the same date (and time if collected), the assessment with the latest database entry date (and time if collected) will be considered as baseline.

6.1.2 *Post Baseline Period*

On-treatment AEs will be defined as AEs with an onset date-time on or after the date-time of the first dose of study treatment (or with an onset date on or after the day of first dose of study treatment if time is not collected or is missing). An AE will be counted as on-treatment if the event occurred within 30 days (or 100 days depending on analysis) of the last dose of study treatment.

On-treatment evaluations (laboratory tests, pulse oximetry, and vital signs) will be defined as evaluations taken after the day (and time, if collected and not missing) of first dose of study

treatment. An evaluation will be counted as on-treatment if it occurred within a safety window of 30 days (or 100 days depending on analysis) of the last dose of study treatment.

Late emergent drug-related AEs will be defined as drug-related AEs with an onset date greater than 100 days after the last dose of study treatment in subjects who are off study treatment.

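### In the visible text, the SAP's worst-grade laboratory table does not use the baseline the SAP defines, so for parameters that may be abnormal at entry it mixes persisting abnormalities with new or worsened ones

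*SAP*

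**What the plan says.** Three places describe the laboratory summary, and they agree with one another. SAP Section 3.1.1 names "specific laboratory abnormalities (worst grade) in each treatment arm". SAP Section 7.5.5 says the parameters "will be summarized using worst grade by treatment group for all treated participants", and adds a by-subject listing. Protocol Section 10.3.2 says "On-study lab parameters including hematology, chemistry, liver function, and renal function will be summarized using worst grade NCI CTCAE v 4.03 criteria".

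SAP Section 6.1.1 separately defines a baseline for laboratory tests. Where there are several valid assessments, the one closest to the day "of the first dose of study treatment will be used as the baseline in the analyses". It also gives a tie-break for assessments made at the same time. Section 6.1.2 classifies later values by timing: "On-treatment evaluations (laboratory tests, pulse oximetry, and vital signs) will be defined as evaluations taken after the day" (and time, where collected) of first dose, up to a set number of days after the last dose. It sets no condition that a value be new, or worse than at baseline.

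**The concern.** A baseline is defined for use in the analyses, yet no visible laboratory analysis uses it. Because a value becomes on-treatment by its date alone, a participant who enters with a mildly raised AST and keeps it appears in the worst-grade table exactly like one whose AST first rose on treatment.

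Under Revised Protocol 01, safety is the only output still planned (protocol Synopsis and Section 4), so the laboratory table is one of the few by-arm summaries the report will contain. A reader who takes its rates as abnormalities arising on treatment would read them too high, and could not tell from the table by how much.

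**Working it through.** **Step 1. Can abnormal values be present at entry?** The limits are in protocol Section 6.2, item 3. The panels are in Table 9.4.1-1.

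| Parameter | Excluded at entry | Carry-over into the table |
|---|---|---|
| AST, ALT | above 3.0x ULN | possible from ULN to 3.0x ULN |
| Total bilirubin | above 1.5x ULN (Gilbert Syndrome: must be below 3.0x ULN) | possible up to the limit |
| Creatinine | above 1.5x ULN, or clearance below 40 mL/min | possible up to the limit |
| Hemoglobin | below 9.0 g/dL | possible from 9.0 g/dL up to the lower limit of normal |
| WBC, neutrophils, platelets | below 2000/µL, 1500/µL, 100 x 10³/µL | largely limited; only values milder than the cut-off |
| Methemoglobin | above ULN | essentially none in eligible participants |
| Alkaline phosphatase, lymphocytes, electrolytes | no numeric limit | possible at any grade |

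The documents do not reproduce the CTCAE thresholds. I assume that a value outside the normal limit receives a grade, and that the grade depends on the value itself, since neither document adds a baseline condition.

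**Step 2. How much could it matter?** The plan gives no figure to reproduce, and none of the inputs below is in the documents. For one arm and one parameter, let

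- b = share abnormal at baseline,
- q = share of those whose abnormality persists after first dose,
- e = rate of new abnormality among everyone else.

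Then

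- any-grade rate = bq + (1 − bq)e
- carried-over share of that rate = bq / rate

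For example, with bq = 5% and e = 10%: 0.05 + 0.95 × 0.10 = 0.145, and 0.05 / 0.145 = 34.5%.

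| bq (assumed) | Rate, e = 10% | Carried over | Rate, e = 20% | Carried over |
|---|---|---|---|---|
| 2% | 11.8% | 16.9% | 21.6% | 9.3% |
| 5% | 14.5% | 34.5% | 24.0% | 20.8% |
| 10% | 19.0% | 52.6% | 28.0% | 35.7% |
| 20% | 28.0% | 71.4% | 36.0% | 55.6% |

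The table cannot separate the components. A 19.0% rate arises from bq = 10% with e = 10%, and equally from bq = 0 with e = 19%. The carried-over share includes people whose persisting abnormality later worsened, so it overstates the purely unchanged cases. Where b = 0 there is no effect.

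**Step 3. What happens between arms?** With 1:1 randomization, bq should be similar in the two arms on average. With bq equal,

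- risk difference = (1 − bq)(e₁ − e₀)

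For e₁ = 20% and e₀ = 10%, the 10-point difference becomes 9.8, 9.5, 9.0 or 8.0 points at bq = 2%, 5%, 10% or 20%. A ratio moves more: at bq = 10% it falls from 20/10 = 2.00 to 28.0/19.0 = 1.47. The direction is unchanged in every case.

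**The case against.** Five points stand on the other side.

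- **The plan is consistent.** SAP Section 7.5.5 delivers what SAP Section 3.1.1 and protocol Section 10.3.2 specify. No stated objective needs change from baseline, and no formal laboratory contrast is visibly planned. This stands: the point is an improvement. A reader might infer that the SAP departs from the protocol, but it does not.
- **Adverse event tables cover part of it.** Protocol Section 9.2.7 sends to the event forms "Any laboratory test result that is clinically significant or meets the definition of an SAE", together with abnormalities that led to delay, discontinuation or corrective therapy. Appendix 3 counts as adverse events abnormal results, "including those that worsen from baseline, considered clinically significant in the medical and scientific judgment of the investigator". These are tabulated by arm under SAP Sections 7.5.2 and 7.5.4. What is left is graded worsening that was not judged clinically significant and prompted no action. The by-subject laboratory listing may allow case review, but it gives no by-arm count.
- **Some text is not available.** A redacted block follows Section 7.5.5, and SAP Section 10 places the table mock-ups in a Data Presentation Plan that is not part of these documents. A reader might infer that the whole plan lacks a baseline display. The documents cannot show that. The Section 7.5.5 method is itself legible, so the point holds for the visible text, and the remedy is conditional.
- **The report is deliberately short.** Several analyses are dropped as unnecessary for a synoptic report. Laboratory analysis is not among them, but brevity is a fair reason to keep any addition small.
- **Not every parameter is affected.** A reader might infer that the entire laboratory table is uninterpretable. It is not. Methemoglobin, which protocol Section 7.4.6 links to BMS-986205, is excluded above ULN at entry, so a later rise above ULN in an eligible participant is new.

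SAP Section 7.5.5 also does not say whether the 30-day or the 100-day window of Section 6.1.2 applies to laboratory values. That merits a clarification, but it is separate and lends no support to this point.

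**Conclusion.** The point holds as a minor one, limited to the visible text. For parameters on which an abnormal value is allowed at entry, the by-arm worst-grade table combines persisting abnormalities with new or worsened ones, although the SAP already defines the baseline needed to separate them.

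The effect is to raise descriptive rates in both arms, mainly at low grades where an entry limit applies and possibly at any grade where none does. The amount is unknown: the percentages above rest wholly on assumed values of b, q and e and are not estimates for this trial. A reader might infer that the table is biased towards one arm. The documents do not support that: assignment was randomized 1:1, so entry abnormalities should be balanced on average, and the consequence is some dilution of an informal comparison with its direction unchanged.

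**What to change.** Keep the worst-grade table. Unless the redacted text or the Data Presentation Plan already provides it, add to SAP Section 7.5.5 wording to this effect:

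> For each graded laboratory parameter, baseline grade (Section 6.1.1) will be cross-tabulated against worst on-treatment grade by treatment group, for participants with at least one on-treatment value. The number and percentage worsening by at least one grade will be given among those with a baseline value. Participants with a missing baseline will appear in a separate row.

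No new data collection is needed: protocol Tables 2-1 and 2-2 already schedule laboratory tests at screening and within 3 calendar days before dosing. The missing-baseline row is there because the footnotes to those tables warn that some assessments may not be captured in the eCRF.

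The cost is a short SAP addition and one further display per graded parameter, not a single table, in a deliberately reduced report. The same edit could name the laboratory window as a housekeeping clarification; 30 days would match Sections 7.5.2 and 7.5.4.
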